6.16. Interim Analyses

An interim database lock and unblinding will occur, and interim analyses will be performed at the time (that is, a cutoff date) the last patient completes Visit 8 (Blinded Dosing Treatment Period [Period 2], Week 16) or ETV. This interim database lock will include all data collected by the cutoff date including the data from the Extended Treatment Period (Period 3) and follow-up data from patients that have begun the Post-Treatment Follow-Up Period (Period 4). The analyses from the Week 16 lock will be treated as a primary analysis because all primary and major secondary study objectives will be assessed at this time.

Additional analyses and snapshots of study data may be performed during the Period 3 or after completion of Period 4 to fulfill the need for regulatory interactions or publication purposes.

6.17. Planned Exploratory Analyses

- To assess the psychometric properties (including reliability, validity, and responsiveness) of the Fatigue NRS in ITT Population.
- To assess the psychometric properties (including reliability, validity, and responsiveness) of the ASAS-HI in ITT Population.
- To explore the impact of each ixekizumab regimen on change from baseline in measures of health utility (EQ-5D); and healthcare resource utilization in the double-blind dosing period and throughout the Extended Treatment Period in the ITT Population.

6.17.1. Psychometric Properties of Fatigue NRS

Unless stated otherwise, the analysis population of the psychometric properties of Fatigue NRS is ITT Population. The psychometric properties of the Fatigue NRS will be evaluated per the following analyses:

- Descriptive Statistics for Fatigue NRS including sample size, mean, median, SD, min, max, % min, % max and % missing, will be provided for the baseline and at Week 16. The number and percentage of Fatigue NRS of 0, 1, ..., and 10 will also be summarized at baseline and at Week 16.
- Convergent and Discriminant validity will be assessed by Pearson correlation and Spearman rank-based correlation coefficient at baseline and at Week 16 between Fatigue NRS and other clinical assessments, including BASFI, BASDAI, Spinal Pain, SF-36 MCS, SF-36 PCS, Patient Global Assessment, and CRP. Cohen's conventions (any correlation greater than 0.5 is large, 0.3 to ≤ 0.5 is moderate, 0.1 to < 0.3 is small, and anything smaller than 0.1 is insubstantial) will be used to interpret the results. It is hypothesized there will be small to moderate correlations at baseline and moderate to large correlations at Week 16 between the Fatigue NRS and all clinical measures, except for CRP. The correlations between Fatigue NRS and CRP at baseline and Week 16 are hypothesized to be small to moderate.
- Known Groups validity of the Fatigue NRS will be evaluated using one-way ANOVA with Scheffe's correction for post-hoc pairwise comparison, in distinguishing Fatigue

NRS scores at baseline and Week 16 among subgroups defined on the basis of ASDAS categories: $ASDAS < 2.1$, $2.1 \leq ASDAS \leq 3.5$ and $ASDAS > 3.5$. If the sample size for any ASDAS category is less than 10% of the total sample size, the ASDAS category will be collapsed with lower category.

- Responsiveness will be evaluated by the correlations of Fatigue NRS changes from baseline at Week 16 (mBOCF) with changes from baseline in other clinical assessments, including BASFI, BASDAI, ASDAS, and Patient Global Assessment at Week 16 (mBOCF). Moderate to large correlations are hypothesized based on Cohens' conventions. Additionally, responsiveness will be evaluated using one-way ANCOVA comparing mean change in Fatigue NRS score (mBOCF) among subgroups defined on the basis of (1) ASAS response status at Week 16: not achieving ASAS20; achieving ASAS20 but not ASAS40; and achieving ASAS40, and (2) BASDAI response status at Week 16 (NRI): BASDAI50 nonresponder and BASDAI50 responder, after controlling for baseline Fatigue NRS. Missing ASAS response status will be treated as not achieving ASAS20. It is hypothesized that an overall statistically significant difference will be observed ($p < 0.05$) with at least one statistically significant subgroup comparisons.
- Test-retest reliability will be assessed in stable patients during the interval between screening and baseline assessment (the 2 assessments will be separated by 4 - 42 days). Stable patients will be defined as those with no more than ± 1.5 point difference in BASDAI ratings between screening and baseline. Intraclass correlation coefficients (ICCs) and change scores will be calculated between the initial and retest to evaluate test-retest reliability. An ICC of 0.60 and above is considered acceptable, and an $ICC \geq 0.7$ is considered substantial agreement (Nunnally and Bernstein 1994). The analysis population for test-retest reliability will be all patients with both screening and baseline assessments.
- The reliability of Fatigue NRS will also be evaluated by the frequency distribution of change in Fatigue NRS from Visit 1 to Visit 2. This analysis will be conducted using the ITT Population and Stable Population defined previously.
- The responder definition of Fatigue NRS will be derived using both distribution-based and anchor-based methods. In the distribution-based method, 1.96 and 2.77 times standard error of measurement (SEM) bears statistical significance (Wyrwich 2004) and are considered a threshold for minimal detectable change. The anchor-based method will utilize a logistic model to explore the relationship between ASAS40 response status at Week 16 (NRI) and the change in Fatigue NRS from baseline at Week 16 (mBOCF). Model adequacy will be evaluated using Concordance Index. Specificity, sensitivity, Youden index, positive predictive value and negative predictive value will also be computed at sequence cut points for change in Fatigue NRS. A Receiver Operating Curve (ROC) will be presented to illustrate the trade-off between sensitivity and specificity. The change in Fatigue NRS associated with the largest Youden index will be considered the responder definition.
- A cumulative probability plot for change in Fatigue NRS from baseline at Week 16 (mBOCF) will be presented by treatment group.

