#### **8.1.2.4. Bath Ankylosing Spondylitis Disease Activity Index**

The BASDAI is a patient-reported assessment consisting of 6 questions that relate to 5 major symptoms relevant to rad-axSpA (Garrett et al. 1994; Sieper et al. 2009): 1) Fatigue, 2) Spinal pain, 3) Peripheral arthritis, 4) Enthesitis, 5) Intensity, and 6) Duration of morning stiffness. Patients need to score each item with a score from 0 to 10 (NRS).

BASDAI50 represents an improvement of  $\geq 50\%$  of the BASDAI score from baseline.

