		Patient Global change from baseline and % improvement from baseline	Change from baseline calculated as: observed patient global – baseline patient global % improvement from baseline calculated as: $100 \times \frac{\text{Baseline} - \text{Observed score}}{\text{Baseline}}$	Missing if baseline or observed value is missing
Spinal Pain	From the ASAS handbook (Sieper et al. 2009), the	Spinal Pain, NRS	Range: 0 to 10 “0” (no pain) and “10” (most severe pain).	Single item, missing if missing

Measure	Description	Variable	Derivation / Comment	Imputation Approach if with Missing Components
	patient is asked to respond to the following 2 questions (on average, last week): 1. “How much pain of your spine due to ankylosing spondylitis do you have?” 2. “How much pain of your spine due to ankylosing spondylitis do you have at night?”		This question is used to derive response for ASAS40, ASAS20, ASAS5/6 and ASAS partial remission.	
		Spinal Pain change from baseline and % improvement from baseline	Change from baseline calculated as: observed spinal pain – baseline spinal pain. % improvement from baseline calculated as: $100 \times \frac{\text{Baseline} - \text{Observed score}}{\text{Baseline}}$	Missing if baseline or observed value is missing
		Spinal Pain at night, NRS	Range: 0 to 10 “0” (no pain) and “10” (most severe pain).	Single item, missing if missing
		Spinal Pain at night change from baseline and % improvement from baseline	Change from baseline calculated as: observed spinal pain at night – baseline spinal pain at night % improvement from baseline calculated as: $100 \times \frac{\text{Baseline} - \text{Observed score}}{\text{Baseline}}$	Missing if baseline or observed value is missing
Bath Ankylosing Spondylitis Disease Activity Index (BASDAI)	The BASDAI is an instrument consisting of 6 questions that relate to 5 major symptoms relevant to rad-axSpA (Garrett et al. 1994; Sieper et al. 2009): 1) Fatigue 2) Spinal pain 3) Peripheral arthritis 4) Enthesitis 5) Intensity of morning stiffness 6) Duration of morning stiffness. Patients need to score each item with a score from 0 to 10 (NRS).	Inflammation	Calculated as: (Q5+Q6)/2 Range: 0 to 10 Q5: “0” (none) and “10” (very severe). Q6: “0” (0 hours) and “10” (≥2 hours).	Missing if both Q5 and Q6 are missing; If Q6 is missing, then use Q5 as inflammation score.

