		BASDAI score	BASDAI = (Q1+Q2+Q3+Q4+inflammation)/5 Range: 0 to 10 “0” (none) and “10” (very severe).	If only Q6 is missing, BASDAI is average of the other 5 questions; missing BASDAI if more missing than just Q6.
		BASDAI and inflammation change from baseline and % improvement from baseline	Change from baseline calculated as: observed score – baseline score % improvement from baseline calculated as: $100 \times \frac{\text{Baseline} - \text{Observed score}}{\text{Baseline}}$	Missing if baseline or observed value is missing
		BASDAI50 – major secondary outcome	BASDAI50 represents an improvement of ≥50% of the BASDAI score from baseline, ie, if the value of % improvement from baseline is ≥50, BASDAI50	Missing if observed value is missing (note: baseline BASDAI is part of inclusion

Measure	Description	Variable	Derivation / Comment	Imputation Approach if with Missing Components
			is met.	criteria therefore should not be missing)
Bath Ankylosing Spondylitis Functional Index (BASFI)	The BASFI establishes a patient’s functional baseline and subsequent response to treatment (Calin et al. 1995). To complete the BASFI, a patient will be asked to rate the difficulty associated with 10 individual basic functional activities. Patients respond to each question using a NRS (range 0 to 10), with a higher score indicating worse functioning.	BASFI score	BASFI score is the mean of the 10 item scores completed on a NRS Range: 0 to 10 “0” (easy) and “10” (impossible).	Missing if >20% scores (ie, >2 of the 10 item scores) are missing
		BASFI change from baseline – major secondary outcome % improvement from baseline	Change from baseline calculated as: observed BASFI – baseline BASFI % improvement from baseline calculated as: $100 \times \frac{Baseline - Observed\ score}{Baseline}$	Missing if baseline or observed value is missing.
High Sensitivity C-Reactive Protein (CRP)	High sensitivity CRP will be the measure of acute phase reactant. It will be measured with a high sensitivity assay at the central laboratory to help assess the effect of ixekizumab on disease activity.	CRP value	Lab values obtained from central lab	Missing if missing
		CRP change from baseline	Change from baseline calculated as: observed CRP – baseline CRP	Missing if observed value is missing (note: if V2 CRP is missing, V1 CRP will be used as baseline).
		CRP ratio of postbaseline to baseline	Calculated as: observed CRP / baseline CRP	

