Fatigue Severity Numeric Rating Scale	The fatigue severity NRS is a patient-administered single-item 11-point horizontal scale anchored at 0 and 10, with 0 representing “no fatigue” and 10 representing “as bad as you can imagine” (Naegeli et al. 2013). Patients rate their fatigue (feeling tired or worn out) by circling the 1 number that describes their worst level of fatigue during the previous 24 hours.	Fatigue Severity NRS	Range: 0 to 10. 0 (no fatigue) and 10 (as bad as you can imagine).	Single item, missing if missing
		Fatigue Severity change from baseline	Calculated as: observed Fatigue Severity NRS – baseline Fatigue Severity NRS	Missing if baseline or observed value is missing
Work Productivity and Activity Impairment Questionnaire—Spondyloarthritis	The Work Productivity Activity Impairment—Spondyloarthritis (WPAI-SpA) consists of 6 questions to determine employment status, hours missed from work because of spondyloarthritis, hours missed from work for other reasons, hours actually worked, the degree to which spondyloarthritis affected work productivity while at work, and the degree to which spondyloarthritis affected activities outside of work. The WPAI-SpA has been validated in	percentage of absenteeism	% work time missed due to problem: $(Q2/(Q2 + Q4))*100$	if Q2 or Q4 is missing, then missing
		percentage of absenteeism - change from baseline	Calculated as: observed value – baseline value	if baseline or observed value is missing, then missing
		percentage of presenteeism	% impairment while working due to problem: $(Q5/10)*100$	if Q5 is missing, then missing
		percentage of presenteeism - change from baseline	Calculated as: observed value – baseline value	if baseline or observed value is missing, then missing
		overall work impairment score	% overall work impairment due to problem: $(Q2/(Q2+ Q4) + [(1-Q2/(Q2+Q4))*(Q5/10)])*100$	if any of Q2, Q4, or Q5 is missing, then missing

Measure	Description	Variable	Derivation / Comment	Imputation Approach if with Missing Components

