6.17.3. Association between Clinical Outcomes and Health Outcome/Quality-of-Life Measures

The objective of the following analysis is to determine whether greater improvement in clinical outcomes from baseline at Week 16, as assessed by categorized ASAS, BASDAI and ASDAS, is associated with larger improvement from baseline at Week 16 in the following continuous health outcome measurements: ASAS-HI, Fatigue NRS, SF-36 PCS, SF-36 MCS, and WPAI-SpA. Association between clinical outcomes and categorical health outcomes, including SF-36 MCS and SF-36 PCS ≥ 2.5 change from baseline, will also be investigated.

Clinical outcomes will be categorized according to [Table RHBV.6.13](#).

Table RHBV.6.13. Categorization of Clinical Outcomes

Categorization	Clinical Outcomes at Week 16		
	ASAS	BASDAI	ASDAS
(1)	ASAS40 Nonresponder	BASDAI50 Nonresponder	ASDAS at least moderate disease(ASDAS \geq 1.3)
(2)	ASAS40 Responder	BASDAI50 Responder	ASDAS inactive disease (ASDAS <1.3)

Abbreviations: ASAS = Assessment of Spondyloarthritis International Society; BASDAI = Bath Ankylosing Spondylitis Disease Activity Index.

Missing categorical clinical outcomes and continuous health outcomes at Week 16 will be imputed by NRI and mBOCF methodology described in Sections [6.3.1](#) and [6.3.2](#), respectively. Missing categorical health outcomes will also be imputed using NRI method as described in Section [6.3.1](#).

The association analysis will be performed using ITT Population with all treatment groups combined and ITT Population with total ixekizumab groups.

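### SAP 6.17.1 validates the Fatigue NRS partly against BASDAI and BASDAI50, which contain a fatigue item, so the BASDAI50 ANCOVA and the baseline correlation can be met through overlap alone

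*SAP*

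**What the plan says.** The Fatigue NRS is a single 0-10 item on which patients rate "their worst level of fatigue during the previous 24 hours" (SAP Table RHBV.6.6). BASDAI also contains fatigue. SAP Table RHBV.6.4 lists its items as "1) Fatigue 2) Spinal pain 3) Peripheral arthritis 4) Enthesitis", followed by two on morning stiffness, and Protocol Section 8.1.2.4 gives the same order. The score is "BASDAI = (Q1+Q2+Q3+Q4+inflammation)/5", so fatigue is one of five equally weighted terms. The response measure uses the full score: "BASDAI50 represents an improvement of ≥50% of the BASDAI score from baseline".

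SAP Section 6.17.1 uses this index in three success criteria for the Fatigue NRS:

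- **Convergent validity.** Correlations are taken "between Fatigue NRS and other clinical assessments, including BASFI, BASDAI, Spinal Pain" and four further measures. They are expected to be small to moderate at baseline (0.1 to 0.5) and moderate to large at Week 16 (at least 0.3), for every measure except CRP.
- **Responsiveness by correlation.** Change in the Fatigue NRS is correlated with change in BASFI, BASDAI, ASDAS and Patient Global, again with at least 0.3 expected.
- **Responsiveness by ANCOVA.** One grouping is ASAS response. The other is "BASDAI response status at Week 16 (NRI): BASDAI50 nonresponder and BASDAI50 responder, after controlling for baseline Fatigue NRS". A difference at p<0.05 is hypothesised.

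Section 6.17.3 relates Fatigue NRS change to clinical outcome "as assessed by categorized ASAS, BASDAI and ASDAS", where the BASDAI category is BASDAI50 (Table RHBV.6.13). Neither section mentions the shared item or plans a version of BASDAI without it.

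**The concern.** A responsiveness test is informative only if it can fail when the scale does not follow clinical change. When the criterion contains a near-duplicate of the scale being tested, part of the association comes from shared content. A patient whose fatigue falls moves towards BASDAI50 through item 1 even if nothing else changes. A significant BASDAI50 comparison could then be reported as evidence that the Fatigue NRS reflects disease activity in general, when it shows partly that two fatigue questions agree. The SAP does not say whether both ANCOVA groupings must be significant, so a result on BASDAI50 alone might be presented as support for responsiveness.

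**Working it through.** The SAP gives no expected coefficient or power for this analysis, so there is no figure of its own to reproduce. The check asks what the planned criteria would show if fatigue were unrelated to the other four BASDAI terms.

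**Inputs from the documents:** about 320 patients (SAP 5.3); the ITT Population (6.17.1); the BASDAI formula and BASDAI50 definition (Table RHBV.6.4); baseline BASDAI of at least 4 (Protocol 5.1); Fatigue NRS change analysed with baseline Fatigue NRS as covariate (6.17.1).

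**Assumed, because the documents do not give them:** correlation r between the Fatigue NRS and item 1 of 0.5 to 0.9; correlation rho among the other four terms of 0.3 to 0.7; item baseline mean 6.8, SD 1.6; item change mean -2.5, SD 2.5. These give BASDAI50 rates of 27-32%.

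**Step 1, correlation built in by the overlap.** With equal SDs, the sum of the five terms has variance 1 + 4 + 12·rho in units of one item's variance, and its covariance with the NRS is r. Hence

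corr(NRS, BASDAI) = r / √(5 + 12·rho)

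- rho 0.7, r 0.5: 0.5/√13.4 = 0.14
- rho 0.5, r 0.8: 0.8/√11 = 0.24
- rho 0.3, r 0.9: 0.9/√8.6 = 0.31
- rho 0.5, NRS identical to item 1 (r = 1): 1/√11 = 0.30

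The same formula applies at baseline, at Week 16 and to change. If the SD of item 1 change is 0.8 or 1.25 times that of the other terms, the values at r = 0.8 run from 0.18 to 0.33 for rho 0.3 to 0.7.

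**Step 2, simulation of the planned tests.** 1,500 runs for each of 15 settings (r from 0.5 to 0.9 in steps of 0.1; rho 0.3, 0.5, 0.7), with integer 0-10 items and no dropout. Nine of the settings:

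| rho | r | mean baseline corr. | mean change corr. | change corr. ≥0.3 | ANCOVA p<0.05, item 1 in | ANCOVA p<0.05, item 1 out |
|---|---|---|---|---|---|---|
| 0.3 | 0.5 | 0.165 | 0.166 | 0.5% | 56.4% | 5.8% |
| 0.3 | 0.8 | 0.264 | 0.268 | 27.5% | 94.3% | 4.5% |
| 0.3 | 0.9 | 0.299 | 0.304 | 53.8% | 97.7% | 4.2% |
| 0.5 | 0.5 | 0.145 | 0.143 | 0.5% | 45.3% | 4.9% |
| 0.5 | 0.8 | 0.232 | 0.235 | 9.5% | 85.7% | 4.7% |
| 0.5 | 0.9 | 0.261 | 0.266 | 25.2% | 92.5% | 4.9% |
| 0.7 | 0.5 | 0.130 | 0.134 | 0.0% | 39.2% | 6.6% |
| 0.7 | 0.8 | 0.208 | 0.212 | 4.2% | 76.5% | 4.4% |
| 0.7 | 0.9 | 0.233 | 0.240 | 11.6% | 86.1% | 5.0% |

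Over all 15 settings the BASDAI50 ANCOVA is significant in 39-98% of runs with item 1 and 4-7% without it. A separate simulation of the same ANCOVA gave 33-97% and 4-7%, so the combined range is 33-98%.

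**Step 3, reading against the SAP's criteria.**

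- *BASDAI50 ANCOVA, p<0.05:* met far more often than the nominal 5%.
- *Baseline correlation, floor 0.1:* the mean is 0.13-0.30, so it is met on average. At the weakest setting (0.13), Fisher's z gives (0.1307 − 0.1003)/(1/√317) = 0.54, or about a 70% chance of exceeding 0.1.
- *Change correlation, at least 0.3:* reached in 0-28% of runs for r up to 0.8, and in 12-54% at r = 0.9. The Week 16 correlation follows the same formula.

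**The case against.** A reader might infer that every BASDAI-based test is bound to succeed, or that the Fatigue NRS would pass validation as a whole even if fatigue had nothing to do with the rest of the disease. The documents support neither reading.

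- Two of the three BASDAI correlation hypotheses (Week 16 and change) need at least 0.3. Overlap alone usually falls short of that, and at rho = 0.5 it gives only 0.30 even if the NRS and item 1 were the same measurement.
- Much of Section 6.17.1 rests on measures without a fatigue item. Known-groups validity uses ASDAS categories, and ASDAS is built from BASDAI items 2, 3 and 6, Patient Global and CRP. Responsiveness also uses BASFI, ASDAS, Patient Global and ASAS20/40 status. The responder definition is anchored on ASAS40. If fatigue were unrelated to disease activity, these would show it.

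Other objections have some weight. Correlating a fatigue scale with an index that includes fatigue is a common form of convergent evidence, and a four-term BASDAI is not the published index. That argues for reporting the reduced version beside the standard one. Section 6.17.3 is an association analysis and not a validation step, so the point there is only about interpretation. The SF-36 also has a vitality domain, and its component scores stay as comparators; the documents do not give item content or weights from which any overlap could be sized.

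What survives is that the BASDAI50 ANCOVA and the baseline BASDAI correlation cannot separate shared content from a real link with the rest of disease activity.

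**Conclusion.** The point holds for the BASDAI50 ANCOVA (roughly 33-98% significant through overlap alone, against about 4-7% without item 1) and for the baseline correlation with BASDAI (0.13-0.30 from overlap, against a floor of 0.1). The Week 16 and change correlations with BASDAI are inflated by the same mechanism but not guaranteed. The fatigue-free anchors are unaffected.

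The percentages depend on the assumed correlations and item distributions, for which the documents give no values. The direction does not: item 1 is in the score by definition. The simulation ignores dropout; carrying NRS values forward while counting dropouts as nonresponders could add some further shared signal. The stable group for test-retest reliability is also defined by BASDAI (within 1.5 points), so the overlap reaches it too; its effect was not sized.

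This is a minor point. Section 6.17 is exploratory and outside the multiplicity-controlled tests, and no treatment comparison changes.

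**What to change.** In Section 6.17.1, and for the Fatigue NRS by BASDAI50 association in Section 6.17.3, add two derived variables: BASDAI without item 1 (the mean of Q2, Q3, Q4 and inflammation) and a response defined as at least 50% improvement in that mean. State that the BASDAI-related validity and responsiveness conclusions rest on this version and on the anchors without a fatigue item. Report the standard BASDAI and BASDAI50 results beside it as descriptive, with a note on the shared item.

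The cost is one extra derived score with its 50% response flag, from item data already collected, and a few lines of SAP text. The drawback is that the reduced index is not the published one, which is why the standard version should stay in the report.
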